Impact of Diabetes Mellitus on Retinal Microvasculature in Patients without Clinical Retinopathy Using Optical Coherence Tomography Angiography

Study Protocol Submitted for Partial Fulfillment
of Master Degree in ophthalmology

Presented by

[name]

M.B.B.CH

Resident of Ophthalmology
Sohag University Hospital.

Supervised by

[name]

Professor of Ophthalmology
Faculty of Medicine, Sohag University

[name]

Assistant Professor of Ophthalmology
Faculty of Medicine, Sohag University.

[name]

Lecturer of Ophthalmology
Faculty of Medicine, Sohag University.

Sohag University
2024

Introduction

Diabetic retinopathy (DR) is a common microvascular complication of diabetes mellitus (DM) and is the leading cause of preventable blindness in working aged people [1].

Fluorescein angiography (FA) is the gold standard investigation for evaluation of Diabetic Retinopathy, yet it is time-consuming and requires invasive intravenous dye administration that may cause various reactions such as vomiting and urticaria [2].

The advent of Optical Coherence Tomography Angiography (OCTA) overcame these disadvantages and added value of imaging rapid and high-resolution images of the retinal microvasculature without intravenous dye administration [3, 4].

OCTA identifies features of preclinical retinopathy that are not detectable by clinical examination and evaluates early ischemic changes as enlarged foveal avascular zones (FAZ) [5-8] , reduced vessel density [8, 9] that are reported to present without clinical retinopathy and also microaneurysm formation which is the most common early clinically visible manifestation of DR [10].

Duration of diabetes has been reported to be a strong predictor for the progression of DR as persistent elevated blood glucose level gradually leads to weakening of the walls of small retinal blood vessels leading to tiny bulges and even leakage [11, 12].

Aim of the work

To assess the impact of duration of DM on OCTA parameters in diabetic patients without clinical Diabetic retinopathy.

Patients and Methods

Study design: Observational, Cross-sectional study.

Study setting: Sohag University Hospital, department of Ophthalmology.

Study population: patients will be recruited from diabetics who will present for retinopathy screening examination at outpatient clinic of Sohag University Hospital.

Sample size determination: every group would include from 60 to 80 eyes calculated by Yamane's formula: $n = N / (1 + N) e^2$, where n = the sample size, N = the population of the study and e = the margin error in the calculation.

The study will be conducted after acquiring the approval of the Medical Research Ethics Committee in the Faculty of Medicine, Sohag University considering that all study participants will be carefully cognized with the nature, presentation and potential consequences of the disease, investigation options and importance of regular follow up and tight control by an informed consent.

Inclusion criteria:

- 1) Age : Above 40 years old
- 2) Type of DM: Type 2.
- 3) Fundus examination: no macular edema or other signs of clinical retinopathy.

Exclusion criteria:

- 1) Age : below 40 years old
- 2) Ocular history : any history of significant ocular injury or disease that could affect the retinal microvasculature such as retinal vascular occlusion, glaucoma, or vitreo-macular disease, as such conditions have also been noted to show sub-clinical OCTA changes [13, 14].
- 3) Fundus examination: macular edema or any other signs of clinical retinopathy.

Procedure: patients recruited for the study will be subjected to the following:

- Personal history: including name, age, sex, occupation and residency.
- Medical history: including duration of DM, type of DM, use of DM medications, most recent hemoglobin A1C and presence of comorbid diseases.
- Ocular examination: including extra-ocular examination, anterior segment examination, visual acuity assessment, IOP measurement and posterior segment examination.

Signs of diabetic retinopathy to be detected include; Micro-aneurysm, Dot and Blot hemorrhages, Flame-shaped splinter hemorrhages, Retinal edema and hard exudates, Cotton-wool spots, venous loops and venous and Intra-retinal microvascular abnormalities (IRMA).

Patients who meet the inclusion criteria will be divided into three groups depending on the duration of diabetes: 0–5 years (short), 6–10 years (medium), and more than 10 years (long). Fourth control group of patients who meet the criteria and don't have DM will be included.

OCTA images will be obtained for the patients by a comprehensive wide-field OCT device (Optovue RTVue XR 100 Avanti, Germany) with 6×6 mm field of view centered at the fovea.

One eye will be selected for inclusion from each patient. If both eyes from an individual patient are similar the right eye will be included in the study. The effect of eye motion-related artifacts is minimized using VTRAC eye tracking software [19].

Images to be included in the study will be required to have a signal strength greater than 7, minimal motion artifacts, decentralization from the foveal center of less than 20 μm , and minimal evidence of obscuration by media opacities [20].

Image analysis will be automatically performed by the AngioVue Comprehensive software, which will provide automated segmentation and calculation of retinal microvascular metrics such as FAZ-related and SVD. The analysis will include the inner retina between the inner limiting membrane and an anterior offset from the retinal pigment epithelium of 110 μm . The superficial capillary plexus (SCP) as the superficial 70% of the inner retina, and the deep capillary plexus (DCP) is the remaining 30% [21].

OCTA parameters derived from the SCP and DCP will be classified into two categories:

- (1) FAZ related metrics: FAZ area, FAZ perimeter and FAZ flow density (FD)
- (2) Vessel density-related metrics: superficial vessel density (SVD) and deep vessel density (DVD) in the 6 mm patch (6 mm diameter around the foveal center), 1 mm patch (1 mm diameter around the foveal center), and inner ring (1 mm patch excluding the FAZ) [9, 20].

Statistical Analysis

Statistical analysis will be performed using SPSS software 23 (SPSS, Inc., Chicago, IL, USA). The Shapiro–Wilk test will be used. Comparisons between groups will be made using the Kruskal–Wallis H test or one-way ANOVA test. Differences between two groups will be estimated with a Mann–Whitney U test or t-test. Multivariate linear regression models will be used to analyze potential associations between each OCTA parameter and systemic risk factors. All p values will be based on two-tailed testing and considered to be statistically significant if $p < 0.05$. A Bonferroni correction will be applied when appropriate.

References

- 2) Early Treatment Diabetic Retinopathy Study Research Group. Classification of Diabetic Retinopathy from Fluorescein Angiograms: ETDRS Report Number 11. *Ophthalmology* 1991, 98, 807–822.

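### Yamane's survey formula, given without values for N or e, does not justify 60 to 80 eyes per group for the planned comparisons of OCTA metrics

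*Combined protocol and SAP*

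**What the plan says.** Under Patients and Methods, the sample-size paragraph is a single sentence: "every group would include from 60 to 80 eyes calculated by Yamane's formula". It prints the formula as n = N / (1 + N) e² and explains its terms in words only ("N = the population of the study and e = the margin error in the calculation"). No number for N or e appears anywhere in the protocol.

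The aim is "To assess the impact of duration of DM on OCTA parameters in diabetic patients without clinical Diabetic retinopathy". The Procedure section sets up the groups: "Patients who meet the inclusion criteria will be divided into three groups depending on the duration of diabetes", and then "Fourth control group of patients who meet the criteria and don't have DM will be included". Four groups of 60 to 80 make 240 to 320 eyes. The total is not stated.

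The unit is clear: "One eye will be selected for inclusion from each patient". Images must also pass quality criteria: "Images to be included in the study will be required to have a signal strength greater than 7, minimal motion artifacts", with further limits on centration and media opacity.

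In the Statistical Analysis section, "Comparisons between groups will be made using the Kruskal–Wallis H test or one-way ANOVA test". Two-group differences are assessed by Mann–Whitney or t-test. Testing is two-tailed at 0.05, with Bonferroni correction where judged appropriate; the number of comparisons is not given. The outcomes are continuous FAZ and vessel-density measures.

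**The concern.** The stated basis has two separate gaps.

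- **It cannot be checked.** N and e are undefined numerically, and very different pairs of values give 60 to 80.
- **It answers a different question.** The formula asks how many units to sample from a finite population so that one estimate has a given margin of error. The study asks whether continuous measurements differ between duration groups. A size for that depends on a difference, an SD, alpha and power. None of these enters the formula, and nothing elsewhere in the protocol connects 60 to 80 with the planned tests.

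At stake is whether a reader can tell in advance what duration effect this study is able to find. Patients with clinical retinopathy are excluded, so the changes sought are subclinical and a small difference cannot be ruled out as the quantity of interest.

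**Working it through.** **1. The plan's own figure.** Inputs from the protocol: n = 60 to 80 per group; N and e not given. The usual form of the formula (general statistical knowledge, not in the protocol) is n = N / (1 + N e²), so N = n / (1 − n e²).

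| e (assumed) | N for n = 60 | N for n = 80 |
|---|---|---|
| 5% | 60 / 0.85 = 70.6 | 80 / 0.80 = 100 |
| 10% | 60 / 0.40 = 150 | 80 / 0.20 = 400 |

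For very large N, n tends to 1/e², so e would have to be 1/√60 = 12.9% or 1/√80 = 11.2%. The stated size is attainable, but the inputs used cannot be identified.

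The form as printed has two readings:

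- [N / (1 + N)] × e² is below 1 for any e below 1.
- N / [(1 + N) e²], for N from 60 upward, gives about 98 to 100 at e = 10% and about 393 to 400 at e = 5%.

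Neither gives 60 to 80 at those margins. The misplaced bracket may be a typing or PDF-extraction slip, so it is secondary.

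**2. What 60 to 80 per group can detect.** Inputs from the protocol: one eye per patient, so observations are independent; two-sided alpha 0.05; three duration groups plus a control. Assumed: 80% power, equal group sizes, normal data with a common SD. The protocol gives no SD, so differences are in SD units.

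*Overall ANOVA.* Noncentral F with noncentrality k·n·f², solved for 80% power:

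| Groups | n = 60 | n = 80 |
|---|---|---|
| Three duration groups | f = 0.233 | f = 0.202 |
| All four groups | f = 0.215 | f = 0.186 |

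If the medium-duration mean lies midway between the other two (an assumption), the three means are −g/2, 0 and g/2. Then f = (g/2)·√(2/3) = g/√6, so the short-to-long gap g = f·√6 is 0.57 SD at n = 60 and 0.49 SD at n = 80.

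*Pairwise tests.* Noncentral t with 2n − 2 degrees of freedom and noncentrality d·√(n/2). For Mann–Whitney on normal data, divide d by √(3/π) = 0.977.

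| Comparisons | alpha | t-test, n = 60 / 80 | Mann–Whitney, n = 60 / 80 |
|---|---|---|---|
| One contrast | 0.05 | 0.516 / 0.446 SD | 0.528 / 0.456 SD |
| Three duration pairs, Bonferroni | 0.05/3 | 0.598 / 0.516 SD | 0.612 / 0.528 SD |
| All six pairs, Bonferroni | 0.05/6 | 0.645 / 0.556 SD | 0.660 / 0.569 SD |

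**3. Power for one t-test contrast at alpha 0.05.** The true differences are illustrative; the protocol names none.

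| True difference | n = 60 | n = 80 |
|---|---|---|
| 0.5 SD | 77.5% | 88.2% |
| 0.4 SD | 58.4% | 71.0% |
| 0.3 SD | 37.1% | 47.0% |

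**4. Precision.** The expected 95% CI half-width for a pairwise difference is t(0.975, 2n − 2)·√(2/n). This is 1.980 × √(2/60) = 0.36 SD at n = 60 and 1.975 × √(2/80) = 0.31 SD at n = 80.

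**The case against.** Several points on the other side stand.

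- **No arithmetic error is proved.** The usual formula can give 60 to 80, so this is a missing and unsuitable justification, not a miscalculation. Nor is quoting a range a fault in itself, since the groups could have different N.
- **A reader might infer that the groups are too small.** The documents do not support that. They name no target difference or SD, and 60 to 80 is reasonable for a single contrast of about half an SD.
- **A reader might infer that a non-significant result would be uninterpretable.** That goes too far. Once data exist, a confidence interval for the difference shows which effects remain compatible with them, whatever the sample-size paragraph said. The protocol does not mention confidence intervals, but nothing prevents their use. The harm lies at the planning stage.
- **Part of the remedy is already there.** A range starting at 60 in every group implies a floor, image quality is already a condition of inclusion, and one eye per patient is fixed. Referring to analysable eyes is a clarification.
- **The documents offer no feasibility rationale.** They give no clinic volume or recruitment rate, so feasibility cannot simply be put in place of the formula. Which duration test is primary is for the sponsor to choose.

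None of this supplies N or e, or ties the size to the planned tests.

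**Conclusion.** The concern holds as a fault in the basis of the sample size. The figure of 60 to 80 cannot be reproduced from the protocol, and the formula cited could not justify it for these comparisons even with N and e filled in. Whether the size is adequate remains open: one-contrast power runs from 37.1% (0.3 SD, 60 per group) to 88.2% (0.5 SD, 80 per group), depending on an effect the protocol does not specify.

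The finding that the basis is unsuitable needs no assumption beyond what the formula contains. The detectable differences rest on 80% power, normal data with a common SD and equal groups; the short-to-long gap from the ANOVA also needs the midway assumption. For an observational cross-sectional thesis study this should be fixed, and the fix does not require more patients.

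**What to change.** 1. Remove Yamane's formula as the basis. If it is kept anywhere, correct the bracket to n = N / (1 + N e²).
2. Keep 60 to 80 per group, with 60 as the minimum number of eyes in each group, one per patient, that pass the image-quality criteria.
3. Call the size feasibility-based only if that is true. Otherwise derive it from a target difference, a sourced SD and a stated power.
4. Name one primary OCTA parameter and one primary duration test (overall or a single contrast, the sponsor's choice). Treat the other parameters and comparisons as secondary.
5. State what 60 to 80 per group detects for that test at 80% power, using the matching row above: the overall ANOVA, one contrast, or a Bonferroni-adjusted set of three or six pairs. Convert it to the parameter's own units with a sourced SD, and say whether a difference of that size matters.
6. Report confidence intervals for group differences.

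The cost is a rewritten sample-size paragraph, a short addition to the Statistical Analysis section and the work of finding an SD. Groups, measurements and the 60 to 80 range stay as they are. The downside is a less favourable stated basis: only moderate differences are detectable at 80% power, and the remaining parameters become secondary.

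### Refraction and axial length are neither recorded nor adjusted for, so a difference in eye length between groups could appear as part of a difference in foveal avascular zone (FAZ) size

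*Combined protocol and SAP*

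**What the plan says.** Under Patients and Methods, Procedure, the ocular examination is listed as "including extra-ocular examination, anterior segment examination, visual acuity assessment, IOP measurement and posterior segment examination". Neither refraction nor axial length is named there or anywhere else.

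The ocular exclusion covers "any history of significant ocular injury or disease that could affect the retinal microvasculature such as retinal vascular occlusion, glaucoma, or vitreo-macular disease". It sets no refractive limit. The image acceptance rules concern signal strength, motion, centration and media opacity only.

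Images are taken "with 6×6 mm field of view centered at the fovea". "Image analysis will be automatically performed by the AngioVue Comprehensive software", and no correction for ocular magnification is described. The outcomes include FAZ area, perimeter and flow density, and vessel density in patches of 6 mm and 1 mm diameter and in an inner ring.

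Patients with diabetes are recruited at retinopathy screening and split into three duration groups. The fourth group is non-diabetic patients who meet the criteria; their source is not given and no matching is described. Under Statistical Analysis, groups are compared by ANOVA or Kruskal-Wallis and pairs by t-test or Mann-Whitney, all unadjusted. The linear regression relates each OCTA parameter to systemic risk factors. No ocular covariate is named.

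**The concern.** An OCT scan covers an angle. Labelling it in millimetres requires an assumed eye length. If the software uses one fixed length for everyone, a longer eye shows a smaller FAZ than it really has, and area is affected about twice as much, in relative terms, as perimeter.

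The Introduction names an enlarged FAZ as an early change of preclinical retinopathy, so the artefact would fall on the signal being sought. Longer-eyed controls would exaggerate a diabetic effect; longer-eyed diabetics would hide one. Ordinary ametropia is not a disease of the microvasculature, so the ocular exclusion does not remove it. Because refraction is not in the planned dataset, an imbalance could be neither seen, adjusted for nor ruled out after the study.

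**Working it through.** The plan gives no figure on this point. Its only design figure is 60-80 eyes per group, attributed to Yamane's formula. That cannot be reproduced, because the population size and margin of error are not stated; it is taken here as given.

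**Inputs from the plan:** 60-80 eyes per group; two-sided alpha 0.05; Bonferroni when appropriate, with the number of comparisons not stated.

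**Assumed inputs, not in the plan:**
- the software does not scale for eye length, and FAZ area is reported in mm² (units are not printed);
- true area is proportional to (AL − 1.82)², where AL is axial length in mm, with a reference eye of 24 mm;
- 1 D of axial ametropia corresponds to 0.3-0.4 mm;
- FAZ area has mean 0.30 and SD 0.10 mm²;
- the mean gap between two groups is 1-2 D.

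**Step 1, area change per dioptre.** The relative change is about 2 × ΔAL / (24 − 1.82).
- 2 × 0.3 / 22.18 = 2.7%
- 2 × 0.4 / 22.18 = 3.6%

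A gap of 1-2 D therefore gives 2.7% to 2 × 3.6% = 7.2%, or about 3-7%. Perimeter scales linearly, so it changes by half as much: 0.3 / 22.18 = 1.4% to 0.8 / 22.18 = 3.6%.

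**Step 2, sensitivity to the scaling rule.** With simple proportional scaling, displayed area changes by 1 − (24 / (24 + ΔAL))². For the same gaps of 0.3 and 0.8 mm this is 2.5% and 6.3%. The result does not hinge on the rule chosen.

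**Step 3, in SD units.** 3% of 0.30 is 0.009 mm², and 0.009 / 0.10 = 0.09 SD. 7% of 0.30 is 0.021 mm², or 0.21 SD.

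**Step 4, chance of a spurious pairwise result.** With no true microvascular difference, let λ = δ / √(2/n), where δ is the shift in SD. Then P = Φ(λ − z) + Φ(−λ − z), with z = 1.960 at alpha 0.05.
- δ = 0.09, n = 60: λ = 0.49, P = 0.08
- δ = 0.21, n = 80: λ = 1.33, P = 0.26

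At alpha 0.05/6 (all six pairs of four groups, z = 2.638) the same two cases give about 0.02 and 0.10, against a nominal 0.008.

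**Step 5, against what the study can detect.** The difference detectable with 80% power is (1.960 + 0.842) × √(2/n): 0.51 SD at n = 60 and 0.44 SD at n = 80. The spurious shift is thus between 0.09/0.51 = 18% and 0.21/0.44 = 48% of it.

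**Step 6, if eye length is balanced.** There is no systematic shift, only added variance. With an assumed eye-length SD of 0.8-1.2 mm, the scale component of FAZ area has an SD of 0.30 × 2 × 0.8 / 22.18 = 0.022 to 0.30 × 2 × 1.2 / 22.18 = 0.032 mm². Removing it would cut the total SD of 0.10 by 1 − √(1 − 0.22²) = 2% to 1 − √(1 − 0.32²) = 5%.

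**The case against.** The strongest reply is that nothing in the plan shows eye length to differ between groups. The stated aim is the effect of diabetes duration. All three duration groups come from the same screening clinic, and there is no evident reason for eye length to vary with duration. The bias therefore bears mainly on the contrast with controls and needs an imbalance that is possible but undocumented. This stands. A reader might infer that the FAZ results will be biased, or that the duration comparisons are compromised; the documents support neither.

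Nearly every number is an assumption, including that the software does not scale. This also stands, and it is why the result is given as a range. A reader might also take the spread for single eyes as the group effect: an eye of 22 mm has true area (20.18/22.18)² = 0.83 of that displayed, and one of 26 mm (24.18/22.18)² = 1.19. Groups are compared on averages, so the 3-7% figure is the relevant one.

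The list of examinations may not be exhaustive, and visual acuity testing may involve refraction. The ocular exclusion might also catch pathological myopia. Both are fair, but neither provides for refraction to be recorded, reported or used.

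Finally, the calculation covers FAZ size only. Vessel density is affected only through the true size of the measured patch, and it should not be read as biased by a similar amount.

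**Conclusion.** The omission is clear; its consequence is conditional. Should controls and diabetics differ by a mean of 1-2 D of axial ametropia, and should the software not scale for eye length, FAZ area would differ spuriously by about 3-7% (0.09-0.21 SD). One unadjusted pairwise test would then reach p<0.05 in roughly 8-26% of studies with no true difference. With balanced eye length the cost is a slight loss of precision. This does not undermine the study or its duration aim. It is an inexpensive improvement, worth settling before recruitment because the planned dataset would hold nothing from which to check balance later.

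**What to change.** 1. In Procedure, add spherical equivalent of the study eye, recorded at the visual acuity assessment in all four groups. Record axial length too where biometry is already available.
2. Report it by group with the other baseline characteristics.
3. In Statistical Analysis, enter spherical equivalent as a covariate in the linear models for FAZ area and perimeter. Include study group in those models, so that the adjustment reaches the group comparison. Use axial length instead for the eyes that have it.
4. Repeat the adjustment for vessel density as a sensitivity analysis.
5. If a refractive limit is wanted, state it in advance and apply it equally to all four groups. The fix does not depend on one.

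The cost is one routine variable and, if a limit is set, a few exclusions and a slightly narrower population. Spherical equivalent is an imperfect proxy for eye length in people over 40, because lens changes also alter refraction. Adjustment will therefore reduce the scale effect, not remove it, and axial length is the better variable where it exists.

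### The aim is the effect of diabetes duration, but the plan tests it by an unadjusted comparison of duration bands and never says that duration in years enters the regression

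*Combined protocol and SAP*

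**What the plan says.** The Aim of the work is "To assess the impact of duration of DM on OCTA parameters in diabetic patients without clinical Diabetic retinopathy".

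Under Patients and Methods, "Patients who meet the inclusion criteria will be divided into three groups depending on the duration of diabetes". The bands are "0–5 years (short), 6–10 years (medium), and more than 10 years (long". A fourth group without diabetes serves as control. Duration comes from the history: "Medical history: including duration of DM, type of DM, use of DM medications". Age and sex are recorded in the personal history. No eligibility criterion refers to duration; the only requirement about the diabetes itself is "Type of DM: Type 2".

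The Statistical Analysis section gives two relevant analyses. The first is "Comparisons between groups will be made using the Kruskal–Wallis H test or one-way ANOVA test", with two-group tests for pairs. The second is "Multivariate linear regression models will be used to analyze potential associations between each OCTA parameter and systemic risk factors". The section does not say whether duration is among those risk factors, whether it would enter in years or as bands, which covariates are included, or which analysis answers the aim. It also does not say whether the overall group test includes the controls.

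**The concern.** Duration is the exposure, and it is collected as a quantity in years. The analysis most plainly tied to it uses only band membership, in a test that ignores the order of the bands and adjusts for nothing. Two things are at stake.

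- **Confounding.** Patients with longer diabetes tend to be older. Eligibility sets a lower age limit but no upper one, and no matching is planned. A difference between bands could therefore partly reflect age, and the ANOVA or Kruskal–Wallis test cannot separate the two.
- **Precision.** If the effect is roughly a trend, cutting duration into three discards the variation within bands and spends two degrees of freedom where one would do.

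The regression that could deal with both is already planned, but the text does not commit it to duration. There is also a smaller problem of definition: the first band ends at 5, the second starts at 6, and nothing says how part-years are recorded.

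**Working it through.** **The plan's own figure.** The plan gives no power, effect size or SD. Its 60 to 80 eyes per group come from Yamane's formula with neither N nor e stated, so the figure can be neither reproduced nor refuted. Only its midpoint is used here.

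**Inputs from the document.** Three diabetic bands; n = 70 per band (midpoint of 60 to 80; one eye per patient), so 210 in total; two-sided alpha 0.05.

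**Assumptions.** Durations uniform within bands on 0–5, 6–10 and 10–20 years; residual SD 1; linear slope b of 0.02, 0.03 or 0.04 SD per year.

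**Step 1: variance of duration.**
- Band means are 2.5, 8 and 15, and the overall mean is 8.5.
- Between bands: (6² + 0.5² + 6.5²)/3 = 78.5/3 = 26.17.
- Within bands: (5²/12 + 4²/12 + 10²/12)/3 = 11.75/3 = 3.92.
- Total: 30.08. The bands keep 26.17/30.08 = 87% of it.

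**Step 2: power.**
- Simple regression: noncentrality 210 × b² × 30.08, on 1 and 208 df.
- Three-band ANOVA: noncentrality 210 × b² × 26.17/(1 + 3.92b²), on 2 and 207 df.

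| Slope (SD/year) | Noncentrality, ANOVA | Power, ANOVA | Noncentrality, regression | Power, regression |
|---|---|---|---|---|
| 0.02 | 2.19 | 24% | 2.53 | 35% |
| 0.03 | 4.93 | 49% | 5.69 | 66% |
| 0.04 | 8.74 | 75% | 10.11 | 89% |

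Simulation (4,000 runs per slope) gives 24, 50, 75% against 35, 66, 88%, which agrees within simulation error.

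**Step 3: sensitivity to the assumptions (ANOVA against regression, same three slopes).**
- n = 60: 21/44/68% against 32/60/83%.
- n = 80: 27/53/80% against 39/72/91%.
- Long band ending at 15 years: 17/33/54% against 24/46/70%.
- Long band ending at 25 years: 35/67/89% against 51/83/97%.
- Duration truncated to whole years: regression essentially unchanged at 35/66/89%, so exact dates are not needed.

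**Step 4: effect of adjusting for age.** With correlation r between age and duration, and residual SD held at 1, the regression noncentrality is multiplied by (1 − r²). At the middle slope, r = 0.3 gives 5.69 × 0.91 = 5.18 and r = 0.5 gives 5.69 × 0.75 = 4.27. Power for the three slopes, on 1 and 206 df with age and sex in the model:
- r = 0.3: about 33/62/86%.
- r = 0.5: about 28/54/78%.
- r = 0.6 (factor 0.64): about 24/48/72%, so the lead over the unadjusted ANOVA is gone.

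A band comparison adjusted for age would lose power too. The document gives no value of r.

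**Step 5: the bands under different recording rules.**

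| Duration (years) | Exact | Completed years | Nearest year | Rounded up |
|---|---|---|---|---|
| 5.5 | none | short | medium | medium |
| 10.0 | medium | medium | medium | medium |
| 10.25 | long | medium | medium | long |
| 10.5 | long | medium | long | long |

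With exact durations only the interval between 5 and 6 years is uncovered. Under assumed distributions (uniform on 0–20; exponential with mean 5, 8 or 10; gamma with shape 2 and mean 8) that is about 5 to 9% of diabetic patients. With any whole-year rule it is 0%.

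**The case against.** The best defence is that bands are a legitimate design choice and that a linear model favours regression by construction. This stands in part. With a step of 0.3, 0.4 or 0.5 SD exactly at 5 years, simulated power in the same design is 43/68/87% for ANOVA against 36/56/75% for regression. With the step at 10 years it is 43/67/87% against 40/62/81%. These figures carry a point or two of simulation error. The document states no dose-response shape. However, the Introduction describes vessel-wall damage as building up gradually with persistent high glucose, which fits a trend better than a jump at a cut-point. Keeping the band comparison covers the other case.

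It can also be said that regression is already planned and that duration, called a strong predictor in the Introduction, would naturally be in it. That is plausible, and a reader should not infer that duration is excluded. The text is simply silent, so the regression cannot be credited as the analysis of the aim.

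On the bands, a reader might infer that patients are misassigned at both cut-points, or that no way of recording duration makes the three bands work. The document does not support either reading. In whole years the bands are exhaustive and mutually exclusive. The gap at 5 to 6 years needs fractional recording, while a shift of 10-to-11-year patients into the medium band needs rounding. The two shares arise under opposite conventions and should not be added. Any single rule does little harm: with durations uniform on 0–20 years (assumed), the short and long bands differ by 12.5 years on average under every rule in the table. Nor is biased placement shown, since grouping is described before imaging and the metrics are computed automatically.

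**Conclusion.** The point holds as a worthwhile and cheap improvement, not as an error that invalidates the study. The plan does not commit any adjusted analysis of duration to the aim, although duration, age and sex are all collected.

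Under a linear trend, continuous duration raises power by about 10 to 17 percentage points at n = 70 per band before adjustment. The gain rests on assumed slopes, an assumed spread of durations and a roughly monotone, near-linear effect. It shrinks as age and duration become more correlated, and reverses modestly if the effect is a step at a cut-point. The case for adjusting for age rests on confounding and does not depend on the power gain.

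The band wording is a minor clarification: the group of a patient with between 5 and 6 years of diabetes is undefined or depends on an unstated rule, and the same rule decides some patients between 10 and 11 years.

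**What to change.** 1. In the Statistical Analysis section, name the main analysis of the aim: in the diabetic patients, linear regression of each OCTA parameter on duration in years as a continuous term, adjusted for age and sex. The controls have no duration and stay in the group comparisons. The other systemic risk factors can remain in the further models already planned.
2. Keep the ANOVA or Kruskal–Wallis comparison of bands as descriptive, and show the band means beside the fitted line as a check on shape.
3. Write the bands as 5 years or less, more than 5 up to and including 10, and more than 10; or state one whole-year recording rule. Say from what date duration is counted.

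The cost is a few sentences, and no additional data or visits. The price is the assumption of a roughly monotone, near-linear trend, which item 2 makes visible. Fixing these definitions before the measurements are analysed also removes any choice over group membership or model form.
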